9.3. WITHDRAWAL CRITERIA

If, during the clinical investigation, a subject must be prematurely withdrawn, the procedures outlined in this section must be followed. These procedures should not interfere with the initiation of any new treatments that are necessary to treat a subject's condition. Information on all withdrawn subjects will be documented.

Subjects may be withdrawn from the clinical investigation for any of the following reasons:

- a. Subject Withdrawal: A subject may voluntarily withdraw from the clinical investigation at any time and for any reason. The subject should be asked when possible, and without any form of coercion, the reason for his/her decision. If the participant withdraws from the clinical investigation completely, then data collected up until the point of withdrawal will be included in the final analysis. Subjects who decline to continue to take part will be given the opportunity to discuss/inform the research team of the reasoning behind their decision not to take part.
- b. Lost to Follow-Up (LTFU): A subject will be considered LTFU after all reasonable efforts have been made to contact the subject and request his/her continued participation in the clinical investigation. All attempts to contact the subject must be documented and should include at least two attempts to contact the subject by phone and one attempt via a certified letter. Data collected up until the point where the subject is LTFU will be included in the final analysis.
- c. Removal of Device or Adverse Event/Incident: The discontinuation of a subject's participation in the clinical investigation due to the removal of the Tibial Nail of the T2 Alpha Tibia Nailing System or Adverse Event/incident that prohibits his/her continued participation must be fully explained. All available information concerning the removal of the device or Adverse

Event/incident should be provided. Data collected up until the point of removal or Adverse Event/incident will be included in the final analysis.

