- d. Death: The discontinuation of a subject's participation in the clinical investigation due to death must be fully explained. All available information concerning the death should be provided. Removal of a subject from continued follow-up in the clinical investigation due to death will not be considered a device failure unless the death is directly caused by, or attributable to, the T2 Tibia Nailing System. Data collected up until the point of death will be included in the final analysis.
- e. Other: A subject may be withdrawn by the Investigator if he/she believes that it is in the best interest of the subject or the IRB/EC may determine that a subject's continued participation in the clinical investigation represents an unacceptable risk to the subject. The Sponsor must be notified immediately if this occurs. All data collected up until the point of withdrawal or IRB/EC determination will be included in the final analysis.

A subject may also be withdrawn if the subject is non-compliant with the clinical investigation procedures or visits, or if a selection criteria violation is noted after the subject received the clinical investigation treatment and it is determined that the subject should be discontinued. All data collected up until the point of withdrawal will be included in the final analysis.

10. Clinical Investigation Evaluations, Procedures and Assessments

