10.4. FOLLOW-UP EVALUATIONS

The follow-up evaluations will occur at 3 Months, 6 Months and 12 Months after the index procedure and include an assessment of device-related adverse events/incidents, evaluation using the SF-36 PCS and MCS scores, as well as clinical assessment of bone consolidation. Investigators should consider weight-bearing, pain and imaging when assessing bone consolidation. See the section below for visit windows and a list of assessments to be performed at each visit.

100 St. 100 St.

Investigative site personnel will contact subjects prior to their scheduled follow-up evaluations to encourage compliance with clinical investigation visits and participation.

If a subject misses a visit and is outside of the visit window, every effort should be made to collect data instead of noting the visit as missed.

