10.5. SCHEDULE OF EVENTS

Assessment	Initial Assessment	3 Months a, b (+/-2 weeks)	6 Months a, b (+/-3 weeks)	12 Months ^b (+/-4 weeks)
Informed Consent	X ^c			
Demographics & Medical History	X			
Inclusion/Exclusion	X			
Primary Diagnosis	X			
Surgical Procedure	X			
Clinical Assessment of Bone Consolidation d, e		X	X	X
SF-36v2 (PCS & MCS)	X ^f	X	X g	X g
Subject Disposition h		X	X	X

Device-Related Adverse Events/Incidents & Reoperations will be collected throughout the course of the Clinical Investigation.

- a. Follow-up visit schedule to reflect Institutions' Standard of Care practices
- b. If the subject missed a visit and outside of visit window, every effort should be made to collect data instead of noting visit as missed. Visit windows are calculated from the index event, and not from the previous visit.
- c. Informed consent must be obtained prior to enrollment in the study (i.e., prior to performance of any study-related activities).
- d. Once bone consolidation is observed, assessment no longer needs to be conducted at the additional follow-up visits.
- e. Investigators should consider weight-bearing, pain and imaging when assessing bone consolidation.
- f. SF-36v2 evaluation must be collected post-informed consent.
- g. If bone consolidation is previously observed at the previous follow-up visit, evaluation is to be collected via phone.
- h. Subject Disposition assessment would occur at any time point for subject withdrawal prior to the completion of the clinical investigation.

0.00

11. Statistical Methods

The Statistical Analysis Plan (SAP) lists all variables/questions within this clinical investigation. Therefore, no additional "evaluation" chapter is required and needed for this CIP.

Data will be captured via IBM Merge EDC system and statistical analysis will be performed using IBM SPSS. All statistical hypotheses tests will be with confidence levels (1- α) of 95% and power (1- β) of 80%. The significance level (α) is 0.05 and the beta-value (β) is set to 0.20. Therefore, p-values \leq 0.05 will indicate statistical significance.

Results will be presented using summary tables and optionally supported by graphs. For detailed information per variable, see SAP.

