With the proposed sample size of 61 subjects, the clinical investigation will have power of 80.0% to yield a statistically significant result.

This computation assumes that the population from which the sample will be drawn has a mean of 43.48 with a standard deviation of 13.04. The observed value will be tested against a theoretical value (constant) of 39.25.

This effect was selected as the smallest effect that would be important to detect, in the sense that any smaller effect would not be of clinical or substantive significance.

A second goal of this clinical investigation is to estimate the mean in the population. On average, a clinical investigation of this design would enable us to report the mean with a precision (95.0% confidence level) of plus/minus 2.77 points.

The precision estimated here is the median precision. Precision will vary as a function of the observed standard deviation (as well as sample size), and in any single clinical investigation will be narrower or wider than this estimate.

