11.3.2. Primary Analysis / Endpoint

This analysis is only part of the final report. The primary endpoint analysis will only be executed once at the end of the clinical investigation and will not be part of any interim or annual reports or presentations given in front of the final report.

The 12 months post-operative results for subjects implanted with the T2 Alpha Tibia Nailing System will be compared to Sanders et al: Semiextended intramedullary nailing of the tibia using a suprapatellar approach: radiographic results and clinical outcomes at a minimum of 12 months follow-up. J Orthop Trauma, 2014; Sun et al: The outcome comparison of the suprapatellar approach and infrapatellar approach for tibia intramedullary nailing. Int Orthop, 2016; and Chan et al: Suprapatellar Versus Infrapatellar Tibial Nail Insertion: A Prospective Randomized Control Pilot Study. J Orthop Trauma, 2016". Specifically, the SF-36 score results reported by Wang, et al. (2017), Sanders, et al. (2014), Sun, et al. (2016) and Chan, et al. (2016) will serve as the control groups for the T2 Alpha Tibia group.

Higher SF-36 PCS and MCS score results are linked to better subject results and vice versa.

The clinical investigation endpoint is non-inferiority to the control, meaning the clinical investigation result should be equal or better than the control. In this clinical investigation, an equal or better SF-36 score result means equal or greater (\geq). As only results from samples will be captured, results are mostly estimates of the true population parameter. These estimates vary by a certain area, where it is expected that the true population parameter falls within. Based on this, it is required to specify a lower limit for the acceptable difference or zone of indifference, denoted as $-\theta$.

Hypotheses were developed to allow for a comparison of the 12 months post-operative SF-36 PCS to evaluate effectiveness / performance. The 12 months post-operative SF-36 PCS is the primary endpoint of this clinical investigation. Hypothesis tests will be one-sided with a significance level α of 5%.

Hypothesis	Equations		Interpretation		
Null (H ₀) $A - B < -\theta$ $T2 \text{ Alpha Tibia (A)} - Co$ $pooled \text{ benchmark result}$		` '	Central tendency of A is inferior to the central tendency of B.		
Alternative (H ₁)	A – B ≥ -θ T2 Alpha Tibia (A) – 0 pooled benchmark res	,	Central tendency of A is non-inferior to the central tendency of B.		
95% H ₀ H ₁					

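### Protocol 9.3 allows withdrawal for missed visits and loss-to-follow-up status before month 12 without requiring the 12-month SF-36 to be sought, and this is not reconciled with the missed-visit rule in 10.4 and 10.5

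*Protocol*

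**What the plan says.** Protocol 9.3 lists the withdrawal reasons. After item (e), an unlettered paragraph adds: "A subject may also be withdrawn if the subject is non-compliant with the clinical investigation procedures or visits". It gives no number of missed visits and no time limit. It covers selection violations found after treatment in the same sentence. Data up to withdrawal enter the final analysis. Nothing is said about obtaining the 12-month SF-36 later.

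Item (b) of the same section, on loss to follow-up, requires all reasonable efforts to reach the subject. The documented attempts "should include at least two attempts to contact the subject by phone and one attempt via a certified letter". No earliest time is given, so the status can be assigned after a failed 3- or 6-month contact. Data are again kept up to that point, and no further attempt at month 12 is mentioned.

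Protocol 10.4 says that when a visit is missed and its window has passed, "every effort should be made to collect data instead of noting the visit as missed". Note b of the 10.5 schedule and of the SAP 4.4 schedule repeats this. Under note a, the 3- and 6-month visits follow each institution's standard of care. Under note g, if consolidation was seen at the previous visit, the 6- and 12-month SF-36 "evaluation is to be collected via phone".

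The primary analysis (Protocol 11.3.2, SAP 6.6) compares the 12-month PCS with 39.25 by a one-sample t-test or sign test. Protocol 11.4 and SAP 4.6 provide only for reporting the number and percentage of missing values. SAP 5.3 refers to the protocol for withdrawal procedures and adds nothing on this point.

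**The concern.** The primary endpoint needs one value per subject, the PCS at month 12. Missing the 3- or 6-month visit does not invalidate that value, and the plan already has a phone route for collecting it in some subjects. Yet for the same event, a missed visit, one section tells the site to keep trying and another lets participation end. No passage says which prevails or whether the missed-visit rule survives withdrawal. Up to five sites could act differently and all comply.

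What is at stake is selective loss. Subjects who attend irregularly may recover differently from those who attend. If they do worse, leaving them out raises the observed mean and favours non-inferiority. The comparator is a fixed constant, so no concurrent arm suffers the same loss to offset it, and no imputation or sensitivity analysis would reveal it. The ITT population is defined as all enrolled subjects, but a subject without a 12-month PCS cannot contribute to the test.

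**Working it through.** **1. The plan's own figure.** Inputs from Protocol 11.1 and 11.3.2: one-sided α = 0.05; the assumed population "has a mean of 43.48 with a standard deviation of 13.04"; and "The observed value will be tested against a theoretical value (constant) of 39.25".

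- Difference: 43.48 − 39.25 = 4.23, which is also the margin.
- One-sample t-test, noncentral t with noncentrality (4.23 / 13.04) × √n: n = 60 gives power 0.799 and n = 61 gives 0.805.
- The planned evaluable number of 61 is reproduced, as is the 0.805 in the SAP's software output.

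**2. Is power threatened?** Planned enrolment is 80 and the drop-out allowance is 20% (SAP 3.2).

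- 0.20 × 80 = 16 lost and 64 observed, power 0.822.
- 80 − 61 = 19 losses (19 / 80 = 23.75%) can occur before the number falls below 61.
- At 25% loss (n = 60) power is 0.799; at 30% (n = 56) it is 0.774.

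The planned allowance is covered.

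**3. Bias from selective loss.** Let a share f of enrolled subjects lack the 12-month PCS, with a mean g points below the observed mean. Then

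mean of all enrolled = (1 − f) × observed mean + f × (observed mean − g) = observed mean − f × g,

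so the observed mean is too high by f × g. The documents give neither f for these clauses nor g, so both are assumptions. The last column is the one-sided rejection rate when the true mean of all enrolled is exactly 39.25, with SD 13.04, n = 80 × (1 − f) and noncentrality (f × g / 13.04) × √n. The nominal rate is 0.05.

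| f (n observed) | g | f × g | share of 4.23 | rejection rate |
|---|---|---|---|---|
| 5% (76) | 3 | 0.15 | 4% | 0.061 |
| 5% (76) | 5 | 0.25 | 6% | 0.070 |
| 5% (76) | 8 | 0.40 | 9% | 0.084 |
| 20% (64) | 3 | 0.60 | 14% | 0.100 |
| 20% (64) | 5 | 1.00 | 24% | 0.150 |
| 20% (64) | 8 | 1.60 | 38% | 0.250 |

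The 5% rows represent 4 of 80 subjects lost through these clauses. The 20% rows apply the plan's whole drop-out allowance, which covers loss of every kind, so they are an upper illustration and do not measure these clauses.

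**4. The passages side by side.** Take a subject who misses the 3- and 6-month visits but could be reached at month 12. Under 10.4 and note b, the site keeps trying to collect data. Under 9.3, the same subject may be withdrawn as non-compliant or, if contact attempts failed earlier, already be classed as lost. After that, no text requires the 12-month SF-36. The phone route in note g does not clearly cover this subject either, because no consolidation was recorded at the previous visit.

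**The case against.** A reader might infer four stronger points that the documents do not support.

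- *Subjects are removed by rule and their 12-month value is never sought.* The wording is permissive, and nothing bars later contact. The value need not be sought, which is less than saying it will not be.
- *Two calls and a letter make a subject lost.* Those three attempts are a documented minimum within a duty to make all reasonable efforts. That is consistent with 10.4. The gap in item (b) is the missing time anchor.
- *Sections 9.3 and 10.4 contradict each other.* Section 10.4 can be read as the default for a missed visit and 9.3 as a discretionary exception. What remains is a tension that the text does not resolve.
- *The bias is 14% to 38% of the margin.* That applies the whole 20% allowance, which rests on a cited study's general loss rate of 11 of 56, to these clauses alone. It also assumes the PCS gap.

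A fair opponent would add that, if nobody uses the discretion, the present text already serves an irregular attender, and that much of the bias risk comes from the absence of any missing-data analysis, which is a separate matter. Both points are right and they limit the size of the concern. They do not remove it: with no fallback in the analysis, preventing avoidable loss matters more, and the text leaves that prevention to site discretion.

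**Conclusion.** The point holds as a gap that should be closed. The protocol permits participation to end for missed visits, sets no earliest time for loss to follow-up, requires no 12-month SF-36 afterwards, and does not reconcile this with its own rule on missed visits. The consequence is avoidable and possibly selective loss of the primary endpoint in a single-arm test that uses observed values only.

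Its size cannot be derived from the documents. With 5% lost this way and a PCS deficit of 3 to 8 points, the upward bias is 0.15 to 0.40 points. That is modest against the margin, but it would lift the false-positive rate from 0.05 to between 0.061 and 0.084. The direction also rests on an assumption: if irregular attenders recovered better, the bias would reverse. The calculation takes the SD as 13.04 and unchanged by the loss. A case built on power would fail, since 64 remain at the planned loss against 61 needed.

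**What to change.** In Protocol 9.3:

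- Record missed visits as protocol deviations and stop treating them as a reason to end participation.
- In item (b), assign final lost-to-follow-up status only after the 12-month contact attempts have failed. A subject not reached at month 3 or 6 stays enrolled.
- State that any subject who has not withdrawn consent, including one discontinued for procedure non-compliance or a selection violation, is still contacted for the 12-month SF-36. Selection violators leave the per-protocol set, but the final report also covers the ITT population, so their value is still useful.

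Allow phone collection for these subjects and align note g in Protocol 10.5 and SAP 4.4, which at present tie phone collection to consolidation seen at the previous visit.

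Treatment, sample size and the primary test do not change. The cost is a protocol wording change with matching SAP text, a few extra calls by site staff, and slightly later closure for subjects who do not respond.

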10.1. METHODS OF ASSIGNING SUBJECTS

No specific methods (e.g. randomization, blinding, or stratification) for assigning subjects are used in this Clinical Investigation Plan. Consecutive subjects at each site meeting all the eligibility criteria will be enrolled in this clinical investigation.

10.2. PROCEDURES

Subjects recruited to this clinical investigation have received the Tibial Nail of the T2 Alpha Tibia Nailing System. Please see the approved Instructions for Use and Operative Technique Manuals for a detailed description of the medical device(s) and instrumentation, intended use information and associated risk. Any additional clinically indicated procedures are permitted as deemed necessary by the clinical investigation investigator.

10.3. INITIAL ASSESSMENT

All subjects presenting for treatment of femoral fractures at the investigative sites will be evaluated for clinical investigation participation based on the eligibility criteria listed in Section 9. Informed consent will be obtained from each subject before any study procedures are performed. Details on obtaining informed consent and related documentation are provided in Section 15.2.

The initial assessment may occur prior to the index surgery, during the subject's hospital stay, or within the 3 months post-surgery. Should the initial assessment occur after the subject's index surgery, data from the subject's medical history, surgical procedure, and the SF-36 PCS and MCS will be collected retrospectively in order to record the subject's pre-operative health status.

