Creation of variable Difference between Date of Surgery [dd.mm.yyyy] and Date of 12 Months Visit [dd.mm.yyyy] in [days] (Variable(s): VISITDT; VISNAME)	Quantitative, ratio	N/A (Analyzed above), used for survivorship		Х	
Create new variable "Grouping variable – First Device Related Adverse Event" (Variable(s): AEEVENT)	Qualitative, nominal	- censored = survivors - events = first (earliest) Device Related Adverse Event		Х	
Create new variable "Combined Time – First Device Related Adverse Event" (Variable(s): AEONSTDT)	Quantitative, ratio	 Use time between surgery and 12 months visit for surviving subjects Use time between surgery and first device related adverse event for subjects with device related adverse event 		Х	
Use variables "Combined Time – First Device Related Adverse Event"	Qualitative,	Case summary with number and percentage of valid		Х	

and "Grouping variable – First Device Related Adverse Event"	nominal Quantitative, ratio	cases/values, missing cases/values (if any) and total cases/values. Kaplan-Meier survival analysis: subject ID, time, status, cumulative proportion, Kaplan-Meier estimate, standard error of KM estimate, number of cumulative events, number of remaining cases, mean for survival time with 95% confidence interval, survival graph bazard graph	
		survival graph, hazard graph.	

Table 6.6.3: Endpoints – Secondary Endpoint Time to (earliest) Device Related Adverse Event / Incident Tables List

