6.7.4. Mortality

For analysis of the time to death or mortality, the Kaplan-Meier method will be used. The times between surgery and the 12 months assessment will be used together with the times between surgery and the date of death. This analysis is part of the final report.

Evaluation	Level of	Recode and Analysis Plan			
Variable / Question	Measurement	Recoue and Analysis I fair			
All Assessments - Morta	lity				
Creation of variable Difference between Date of Surgery [dd.mm.yyyy] and Date of Death [dd.mm.yyyy] in [days]] (Variable(s): VISITDT; DOSEDD)	Quantitative, ratio	Case summary with number and percentage of valid cases/values, missing cases/values (if any) and total cases/values. Mean, median, interquartile range, maximum, minimum, standard deviation, 95% confidence interval for mean, Shapiro-Wilk Test.			
Creation of variable Difference between Date of Surgery [dd.mm.yyyy] and Date of 12 Months Visit [dd.mm.yyyy] in [days] J (Variable(s): VISITDT)	Quantitative, ratio	N/A (Analyzed above), used for survivorship			
Create new variable "Grouping variable - Mortality" (Variable(s): PRIMRSN)	Qualitative, nominal	 - censored = survivors - events = death 			
Create new variable "Combined Time - Mortality" (Variable(s): VISITDT; DOSEDD)	Quantitative, ratio	 Use time between surgery and 12 months visit for surviving subjects Use time between surgery and death for deceased subject 			

Use variables "Combined Time - Mortality" and "Grouping variable - Mortality" Qualitative, nominal Quantitative, ratio	Case summary with number and percentage of valid cases/values, missing cases/values (if any) and total cases/values. Kaplan-Meier survival analysis: subject ID, time, status, cumulative proportion, Kaplan-Meier estimate, standard error of KM estimate, number of cumulative events, number of remaining cases, mean for survival time with 95% confidence interval, survival graph, hazard graph.
--	---

Table 6.7.4: All Assessments – Mortality Tables List

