6.7.5. Revision Surgery

For analysis of the time to the revision surgery, the Kaplan-Meier method will be used. The times between surgery and the 12 months assessment will be used together with the times between surgery and the date of revision (earliest revision in case that one subject experienced more than one revision). This analysis is part of the final report.

Evaluation Variable / Question	Level of Measurement Recode and Analysis Plan				
Adverse Events / Revision Surgery					
Creation of variable Difference between Date of Surgery [dd.mm.yyyy] and Date of First Revision [dd.mm.yyyy] in [days]] (Variable(s): VISITDT)	Quantitative, ratio	Case summary with number and percentage of valid cases/values, missing cases/values (if any) and total cases/values. Mean, median, interquartile range, maximum, minimum, standard deviation, 95% confidence interval for mean, Shapiro-Wilk Test.			
Creation of variable Difference between Date of Surgery [dd.mm.yyyy] and Date of 12 Months Visit [dd.mm.yyyy] in [days] J (Variable(s): VISITDT)	Quantitative, ratio	N/A (Analyzed above), used for survivorship			
Create new variable "Grouping variable – First Revision" (Variable(s): VISITDT)	Qualitative, nominal	 - censored = survivors - events = first (earliest) Revision 			
Create new variable "Combined Time – First Revision" (Variable(s): VISITDT)	Quantitative, ratio	 Use time between surgery and 12 months visit for surviving subjects Use time between surgery and first revision for subjects with revision(s) 			
Use variables "Combined Time – First Revision" and "Grouping variable – First Revision"	Qualitative, nominal Quantitative, ratio	Case summary with number and percentage of valid cases/values, missing cases/values (if any) and total cases/values. Kaplan-Meier survival analysis: subject ID, time, status, cumulative proportion, Kaplan-Meier estimate, standard error of KM estimate, number of cumulative events, number of remaining cases, mean for survival time with 95% confidence interval, survival graph, hazard graph.			

Table 6.7.5: All Assessments – Revision Surgery Tables List

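### Consent is allowed up to 3 months after surgery but Kaplan-Meier time starts at surgery: early mortality is understated, and reoperation and device-event risk may be

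*Protocol*

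**What the plan says.** **Entry.** Protocol 10.3 allows the initial assessment before surgery, in hospital "or within the 3 months post-surgery". The schedule in 10.5 puts consent in that assessment and adds: "Informed consent must be obtained prior to enrollment in the study". Section 10.2 describes the cohort as already implanted: "Subjects recruited to this clinical investigation have received the Tibial Nail of the T2 Alpha Tibia Nailing System".

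**Data on late entrants.** Under 10.3, if the assessment follows surgery, the medical history, "surgical procedure, and the SF-36 PCS and MCS will be collected retrospectively". Device-related events and reoperations are not in that list. Section 10.5 has them collected over the whole investigation, without saying whether this reaches back before consent.

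**Time rule.** For mortality, SAP 6.7.4 says "Use time between surgery and death for deceased subject", and survivors are given the time from surgery to the 12-month visit. SAP Table 6.6.3 says "Use time between surgery and first device related adverse event for subjects with device related adverse event" and, for the rest, "Use time between surgery and 12 months visit for surviving subjects". SAP 6.7.5 applies the same rule to first revision. Neither document uses a consent date, a delayed-entry risk set, a landmark or a sensitivity analysis for late entry.

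**The concern.** A subject who consents in week 10 is counted as at risk from day 0. Someone who died in week 4, before being approached, never signs a consent form. That patient belongs to no analysis population, because the ITT population (Protocol 11.2, SAP 5.1) consists of enrolled, consented subjects. The denominator therefore gains survival time that was certain in advance, and the matching deaths are never seen.

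The period affected is the first three months. That is where peri-operative harm would be expected, and the synopsis says that safety is to be shown through intra-operative and post-operative events. A curve that is too favourable there weakens the safety description, although no hypothesis test depends on it.

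**Working it through.** **1. The plan's own figures.** The plan states no figure for the three Kaplan-Meier analyses. Its only computed design figure, power 0.805 at n = 61, reproduces: a one-sided one-sample t-test at 0.05 with a difference of 4.23 and SD of 13.04 gives 0.8051. It plays no part here.

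**2. Is the window real?** SAP Table 4.4 labels the first visit as operative/discharge, which might suggest early consent only. The text after that table, however, lets pre-operative data be recorded post-operatively as the protocol defines. The SAP therefore does not close the 3-month window. Consecutive enrolment (Protocol 10.1) does not help, because only patients who consent are enrolled.

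**3. Which curves are affected?**
- *Death:* being alive is a condition of consent, so the time from surgery to a late consent is death-free by construction.
- *First device-related event:* a patient can consent after such an event. The SAP dates it by onset (AEONSTDT), so it counts if recorded. Two features could still lose events. Retrospective collection does not name them, and active infection is an exclusion (Protocol 9.2) while deep and superficial infection are foreseeable device events (13.3).
- *Reoperation:* no criterion bars an earlier reoperation as such, but retrospective collection does not name it either. Nail removal is a withdrawal reason (9.3), not an exclusion.

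**4. Size when the event prevents enrolment.** Let *f* be the share of patients approached late, *U* the time from surgery to approach and *S(t)* the true event-free probability. For *t* of 90 days or more,

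naive risk = 1 − *S(t)* / [(1 − *f*) + *f* · E{*S(U)*}].

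Assumptions, none of them in the documents: true risk 5% at 90 days and 10% at 12 months, constant hazard over the first 90 days, and *U* uniform on 0–90 days. Then E{*S(U)*} = 0.05 / (−ln 0.95) = 0.9748. With *f* = 0.5 the denominator is 0.5 + 0.5 × 0.9748 = 0.9874, which gives
- 90 days: 1 − 0.95/0.9874 = 3.79%
- 12 months: 1 − 0.90/0.9874 = 8.85%

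| Share late | Uniform entry: 90 d | Uniform entry: 12 mo | All late entry at day 90: 90 d | All late entry at day 90: 12 mo |
|---|---|---|---|---|
| 0% | 5.0% | 10.0% | 5.0% | 10.0% |
| 25% | 4.40% | 9.43% | 3.80% | 8.86% |
| 50% | 3.79% | 8.85% | 2.56% | 7.69% |
| 75% | 3.17% | 8.27% | 1.30% | 6.49% |
| 100% | 2.54% | 7.67% | 0% | 5.26% |

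Other assumed risks, half late and uniform entry: 1% at 90 days and 2% at 12 months become 0.75% and 1.75%; 10% and 20% become 7.65% and 17.91%.

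**5. Simulation check.** 1,000 runs of 80 subjects, with true risks of 10% at 90 days and 20% at 12 months. With half late, the naive curve averaged 7.8% and 18.1%, and the delayed-entry curve 10.2% and 20.2%. With all late, the naive curve averaged 5.3% and 15.6%, and delayed entry 10.0% and 19.8%. With none late, both gave 9.9% and 19.8%.

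**The case against.** A reader might infer that all three curves contain guaranteed event-free time and that all three need a delayed-entry risk set. The documents do not support that. Only death makes consent impossible. The synopsis includes intra-operative events, which precede any post-operative consent, so some pre-consent capture appears intended. Device events are also assessed at the 3-month visit (Protocol 10.4).

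Entering subjects at consent would discard recorded device events and reoperations with earlier onset. It would also thin the early risk set: with 75% of 80 subjects entering late, 20 are at risk on day 0, so one event then moves the curve by 1/20 = 5 points instead of 1/80 = 1.25. This part of the objection stands, and it is why the remedy differs by curve.

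It is also fair that the curves are descriptive. No test, benchmark or stopping rule uses them. Mortality and reoperation are additional analyses, and the protocol's secondary safety endpoint is incidence, tabulated as proportions in SAP 6.1. Against that, SAP Table 6.6.3 labels time to first device-related event a secondary endpoint. None of this answers the point on mortality, where the time rule is wrong whenever anyone enters late.

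**Conclusion.** For mortality the defect follows from the design: the SAP 6.7.4 rule understates early risk if any subject consents after surgery. For reoperation and first device-related event, understatement is possible, and it turns on a question that the documents leave open: whether events between surgery and a late consent are recorded with their true dates.

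In the half-late, uniform-entry illustration the loss is about a quarter of the 90-day risk (5% to 3.8%) and about 11–12% of the 12-month risk (10% to about 8.9%). It is larger if late entry clusters near 3 months. These figures assume that every event prevents enrolment, which is certain only for death, and they rest on event rates and a late share that the documents do not give. With no late entrants the bias is zero.

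**What to change.** - **SAP 6.7.4 (mortality):** enter each subject in the risk set at the later of surgery and consent date (delayed-entry Kaplan-Meier). No recorded death is lost, since none can precede consent. The method assumes that the timing of consent is unrelated to the risk of death, and the SAP should say so.
- **SAP Table 6.6.3 and 6.7.5:** keep surgery as time zero. State in the protocol and SAP that device-related events and reoperations between surgery and consent are collected back to surgery with true onset dates. Repeat both curves in subjects consented by discharge.
- **All three:** report the number of late entrants and their time from surgery to consent.

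**Cost.** Some SAP and protocol wording and a little programming. The consent form is dated (Protocol 15.2), but the SAP lists no consent-date variable, so one must be added to the analysis data. SAP 4.5 already allows software other than SPSS. The statistical price is a smaller early risk set and wider early intervals for mortality, and fewer subjects in the sensitivity curves.
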